4.1.4.1 Study Medication Administration

Trial medication administration at site visits

Detailed written instructions and training for the use of the Respimat[®] Inhaler and Diskus[®] Inhaler will be given to the patient at Visit 1 (see [Appendices 10.1](#) and [10.2](#)). At Visits 2 - 4 detailed instructions on the use of the devices will be repeated if needed, but patients should not inhale from a training device that day. The investigator or qualified study personnel will observe the inhalation procedure and will reinforce a correct inhalation technique.

At each clinic visit and in this order, oral inhalation of two puffs of the trial medication from the assigned Respimat[®] Inhaler followed by one puff of trial medication from the assigned Diskus[®] Inhaler (inhaled according to the instructions provided in Appendix 10.1 and 10.2) will be self-administered by the patient under the direct supervision of the investigating physician or designee. In addition, the evening dose of one puff from the Diskus[®] will be self-administered by the patient under the direct supervision of the investigating physician or designee at Visits 3 and 4. The utmost care should be taken to ensure that during the treatment phase the study medication is not taken prior to coming to the site. The exact time-point of trial medication inhalation (i.e. end inhalation procedure which consists of one inhalation from the fluticasone propionate+salmeterol Diskus[®]) for both the morning and evening doses on visit days at the site will be captured in the MasterScope[®] CT spirometer.

When planning the time of the morning dose of trial medication at Visit 2, site personnel should discuss with the patient about the preferred regular time of day that the patient will be taking the morning dose of trial medication at home as this will also affect the time the patient will take the evening dose at home.

At Visit 2, the trial medication will be self-administered between 7:00 a.m. and 10:00 a.m. At subsequent clinic visits, the morning dose of trial medication will be self-administered within ± 30 minutes of time of administration at Visit 2. The evening dose of trial medication will be self-administered at home by the patient between 7:00 p.m. and 10:00 p.m., twelve hours (± 30 minutes) after the administration of the morning dose of trial medication.

At Visits 3 and 4 (i.e., 24-hour PFT visits), for the evening dosing, oral inhalation of one puff of medication from the Diskus[®] (inhaled according to the instructions provided in [Appendix 10.2](#)) will be self-administered by the patient between 7:00 p.m. and 10:00 p.m., twelve hours (± 30 minutes) after administration of the morning dose of trial medication. This evening dose will be inhaled after the 11h50min PFT and prior to the 12hr30min PFT time point.

The last administration of the study medication will be taken at the clinic at Visit 4 (EOT) from the Respimat[®] inhaler and Diskus[®] inhaler that is in current use since no new medication treatment boxes will be dispensed at this visit.

Trial medication administration at home

Each morning between clinic visits and in this order, oral inhalation of two inhalations of the trial medication from the assigned Respimat[®] Inhaler and one puff of trial medication from the assigned Diskus[®] Inhaler (inhaled according to the instructions provided in [Appendices 10.1](#) and [10.2](#)) will be self-administered by the patient.

Patients are to be instructed that the morning and evening doses of trial medication will be self-administered within ± 30 minutes of time of administration at Visit 2.

Each evening, one additional inhalation of trial medication from the Diskus[®] Inhaler (inhaled according to the instructions provided in Appendix 10.2) will be self-administered by the patient, twelve hours (± 30 minutes) after administration of the morning dose of trial medication.

If the patient forgets to take the morning dose of trial medication within the specified time window, the patient can take the morning dose up until 12:00 p.m. (noon). After 12:00 p.m. the patient should skip the morning dose and take evening dose per protocol. The patient should then take the next morning dose at the scheduled time the following day. If the patient forgets to take the evening dose of trial medication within the specified time window, the patient can take the evening dose up until 12:00 midnight. After midnight the patient should skip the evening dose and take the next evening dose at the scheduled time the following evening.

Patients are to be instructed that on the day preceding Visits 3 and 4 that the doses of trial medication must be self-administered within ± 30 minutes of time of administration at Visit 2 AND between 7:00 a.m. and 10:00 a.m. for the morning dose to avoid influence on the data collected on the site visit day. Patients should also be instructed that on the day preceding Visits 3 and 4 the evening dose of trial medication must be self-administered within ± 30 minutes of time of administration at Visit 2 AND between 7:00 p.m. and 10:00 p.m. to avoid influence on the data collected on the site visit day.

Table 4.1.4.1: 1 tiotropium+olodaterol and fluticasone+salmeterol treatments

| Treatment Group | Morning Dose | Evening Dose |
|--|--|---|
| Tiotropium+Olodaterol FDC 5µg/5µg | 2 puffs – Tio+Olo 2.5µg/2.5µg inhaler plus 1 puff – placebo fluticasone propionate+salmeterol | 1 puff – placebo fluticasone propionate+salmeterol |
| Fluticasone propionate+salmeterol FDC 250µg/50µg | 2 puffs – Tio+Olo placebo inhaler plus 1 puff fluticasone propionate+salmeterol 250µg/50µg | 1 puff fluticasone propionate+salmeterol 250µg/50µg |

Respimat® and Diskus® Return

The Respimat® and Diskus® Inhalers dispensed for treatment can be used for approximately 30 days each.

All used and unused Respimat® and Diskus® Inhalers dispensed at Visit 2 and 3 must be returned to the patient treatment boxes and returned at Visit 3 and 4 respectively, after administration of trial medication at the site.

Any Respimat® Inhaler or Diskus® Inhaler that has been reported as malfunctioning by a patient or investigator will be returned to Boehringer Ingelheim for investigation. See the ISF for specific instructions and for details regarding drug accountability requirements. A detail of the procedure for the return of used inhalers is provided in [Appendices 10.1](#) and [10.2](#).

4.1.5 Blinding and procedures for unblinding

4.1.5.1 Blinding

Patients, investigators and everyone involved in analyzing or with an interest in this double-blind study will remain blinded with regard to the randomized treatment assignments until after database lock.

Boehringer Ingelheim will generate the randomization scheme using validated randomization software, and prepare and code the medication in a blinded fashion. Study medication will be assigned for the patients via the IRT. Refer to [Section 4.1.5.2](#) for rules for breaking the code for an individual or for all patients in emergency situations.

4.1.5.2 Unblinding and breaking the code

The ability to unblind will be available to the investigator via the IRT. Unblinding must only be used in emergency situations when the identity of the study drug must be known by the investigator to provide appropriate medical treatment. Each site receives a manual from the IRT provider that contains instructions on how to unblind the treatment of a patient via the IRT (via 24-hour Emergency helpline). If possible, the sponsor, i.e. Clinical Monitor Local (CML) and Trial Clinical Monitor (TCM) must be contacted prior to the site unblinding a patient's treatment. Patients unblinded to treatment will be withdrawn from the trial.

4.1.6 Packaging, labelling, and re-supply

Boehringer Ingelheim will provide all study supplies including blinded study medication, open-label Atrovent[®] HFA, open-label ProAir[®] HFA and Respimat[®] and Diskus[®] training kits. They will be packaged and labelled in accordance with the principles of Good Manufacturing Practice (GMP). Re-supply to the sites will be managed via an IRT system, which will also monitor expiry dates of supplies available at the sites.

Training Materials

- Respimat training: Training Respimat[®] Inhaler, placebo cartridges and disposable mouthpieces will be provided for training purposes: A training device may be used for more than one training session. The training Respimat[®] Inhaler can be used until 3 months after first insertion of the cartridge or until the device is empty. The date of the cartridge insertion should be entered on the medication label of the Respimat[®] immediately after the cartridge is inserted. A new mouthpiece should be used for each patient.
- Diskus[®] training: Training placebo Diskus[®] Inhaler kits will be provided for training purposes. The Diskus[®] Inhaler should not be used beyond one month after removal from the moisture-protective foil overwrap, or after all blisters have been used (when indicator reads "0"), whichever comes first. The device should be cleaned with antiseptic wipes, followed by a dry tissue after each patient use.

Open-label supplies = Auxiliary Medicinal Product (AMP)

- Atrovent[®] HFA for use as run-in medication will be provided by BI and purchased locally. This medication (Atrovent[®] HFA) will be provided for use during the LAMA washout prior to the randomization visit, on investigator's discretion.
- ProAir[®] HFA MDI inhalation aerosol (100 µg per actuation) for use as rescue medication during the screening/run-in and treatment period. The rescue medication will be provided by BI and purchased locally.

Blinded study medication = Investigational Medicinal Product (IMP)

All study medication (also containing blinded placebo medication) will be contained in Respimat[®] or Diskus[®] treatment boxes identified with the trial number and a unique medication number.

The treatment boxes will have a tear-off label. This tear-off label will be attached to the drug dispensing log which will be part of the ISF. Examples of the labels are provided in the ISF.

Packaging

- The Respimat[®] treatment box will contain 1 Respimat[®] inhaler plus one drug-filled cartridge and contains sufficient medication for 30 days of treatment. The Respimat[®] inhaler will lock after 60 actuations have been administered and will no longer actuate any medication.
- The Diskus[®] treatment box will contain one Diskus[®] inhaler. Each Diskus[®] contains sufficient medication for 30 days of treatment. The Diskus[®] inhaler will be contained inside a foil pouch which will be heat-sealed and labelled, before being placed into the treatment box.

Labelling

Individual treatment boxes will have a medication identification label and a tear-off label. Each tear-off label should be attached to the drug accountability form which will be part of the ISF. The investigator or designee should complete the following information:

- Date of cartridge insertion, patient number and visit number should be entered at time of cartridge insertion on the inhaler booklet label.
- Investigator's name should be entered at the time of dispensing on the label of the treatment box.

For details of packaging and the description of the label, refer to the ISF.

Medication Dispensing

The assignment of Respimat[®] and Diskus[®] treatment boxes dispensed at the beginning of each treatment visit (Visit 2 and Visit 3) will be handled by an IRT system.

At randomisation (Visit 2), the site staff will phone or use the web to access the IRT and obtain medication numbers for each of the 3 Respimat[®] treatment kits and 3 Diskus[®] treatment kits to be dispensed to the patient for daily use during the 6 weeks between visits. Two of the treatment kits will be used by the patient and the third is a reserve kit.

The Respimat[®] and Diskus[®] medication and reserve kits will have unique medication numbers. One Respimat[®] inhaler will be primed by the site staff (see [Section 4.1.4](#)) and used to dose the patient at that site visit, and will continue to be used at home until 30 days of

treatment has been reached. The Diskus[®] Inhaler does not have to be primed and will be used for 30 days of treatment.

The second Respimat[®] kit will be primed and used by the patient to cover the remaining weeks until the next visit. The third Respimat[®] kit and the third Diskus[®] kit are reserve medication. This is to allow the patient the flexibility of not having to return to the site immediately to replace a lost or malfunctioning Respimat[®] or Diskus[®].

NOTE: The Respimat[®] Inhaler and drug-filled cartridge that is not yet in use by the patient (including the reserve) should not be assembled prior to leaving the site. These devices must be assembled and primed by the patient at home when needed. The Investigator or designee should fill in the investigator's name on the medication label of all three Respimat[®] and Diskus[®] treatment boxes at time of dispensing to the patient (Visit 2 and 3 respectively).

Please note that the date of cartridge insertion should be entered (label of Respimat[®] inhaler only) at time of cartridge insertion only, i.e. for the first Respimat[®] inhaler this is entered by site staff (during Visit 2 and 3), for the second Respimat[®] inhaler the patient is advised to do so when assembling this device at home during the treatment period, as well as for the third (reserve) Respimat[®] inhaler, if necessary.

Re-Supply

Each site will receive a first supply after the first patient is registered in the IRT and will be resupplied upon demand by the IRT.

4.1.7 Storage conditions

All clinical trial supplies will be stored in a locked, secure cabinet and must be kept under the recommended storage conditions on the medication label. Clinical trial supplies may only be dispensed to trial subjects according to the protocol.

The Respimat[®] Inhaler and cartridges and Diskus[®] Inhaler should be stored as indicated on the country specific booklet page. A temperature log must be maintained at the site to make certain that the drug supplies are stored at the correct temperature as specified in storage conditions for trial medication (STORM) document. If the storage conditions are found to be outside the specified range, immediately contact the local clinical monitor.

Drug supplies will be kept in their original packaging and in a secure limited access storage area according to the recommended storage conditions on the medication label. A temperature log must be maintained for documentation.

Further details are provided in the STORM document and on the country-specific labels, a sample of which will be part of the ISF.

Throughout the trial, trial drug receipt and rescue drug receipt, usage and return must be documented and verified. Any discrepancies in drug supplies will be noted and explained.

4.1.8 Drug accountability

The investigator and/or pharmacist and/or investigational drug storage manager will receive the investigational drugs delivered by the sponsor when the following requirements are fulfilled:

- Approval of the trial protocol by the IRB / ethics committee,
- Availability of a signed and dated clinical trial contract between the sponsor and the head of the investigational site,
- Approval/notification of the regulatory authority, e.g. competent authority,
- Availability of the curriculum vitae of the principal Investigator,
- Availability of a signed and dated clinical trial protocol,
- Availability of the proof of a medical license for the principal Investigator,
- Availability of Form FDA 1572

The investigator and/or pharmacist and/or investigational drug storage manager must maintain records of:

- the product's delivery to the trial site,
- the inventory at the site,
- the use by each patient,
- the return to the sponsor or alternative disposal of unused products. If applicable, the sponsor or warehouse / drug distribution centre will maintain records of the disposal,
- dates, quantities, batch / serial numbers, expiry ('use-by') dates, and the unique code numbers assigned to the investigational product and trial patients,
- adequate documentation that the patients were provided the doses specified by the CTP,
- reconciliation of all investigational products received from the sponsor.

At the time of return to the sponsor and/or appointed CRO, the investigator / pharmacist / investigational drug storage manager must verify that all unused or partially used drug supplies have been returned by the clinical trial patient and that no remaining supplies are in the Investigator's possession.

The investigator/ pharmacist will record on the drug accountability forms the following information:

For Respimat[®] inhaler and Diskus[®] inhaler

- dates (dispense and return)
- dispenser's initials
- batch/serial numbers
- expiry dates
- the unique Respimat[®] and Diskus[®] treatment box number assigned by IRT
- trial patient number

It is important to enter the date of priming on the medication label of the Respimat[®] see [Section 4.1.6](#).

Rescue medication and run-in medication

AMP accountability forms will be provided for albuterol (rescue medication) and Atrovent HFA (run-in medication-if applicable). This record will include:

- dates (dispense and return)
- dispenser's initials
- quantities
- batch/serial numbers
- expiry dates
- trial patient number

Patients will be asked to return all run-in medication (if dispensed, at Visit 2) and used /unused rescue medication and inhalers at each clinic visit. Source data documentation and full drug accountability in regard to dispensed and returned medication to investigational site and to patients is required. Only used inhalers will be replaced at each clinic visit. For further details, please refer to [Section 4.2.1](#).

4.2 OTHER TREATMENTS, EMERGENCY PROCEDURES, RESTRICTIONS

4.2.1 Rescue Medication, emergency procedures and additional treatments

4.2.1.1 Rescue medication

Administration of rescue medication can occur at any point during the trial as deemed necessary by the patient or the investigator. Open label albuterol HFA MDI (100 µg per actuation) will be provided as rescue medication by BI; only the albuterol MDI provided by BI is allowed for rescue medication use. If the patient requires rescue medication during the pulmonary function test (PFT) days (Visits 2, 3 and 4), the PFTs will be continued if possible. The medication used, route and 24-hour clock time of administration will be recorded on the Rescue Medication eCRF page. The visit should not be re-scheduled. In the case where the investigator decides to discontinue a patient from a PFT visit or rescue treatment is administered please contact the sponsor (e.g. the Local Clinical Monitor) prior to discontinuing the patient.

Rescue Medication on and before Pulmonary Function Test Days

All test-day rescue medication administered before the conclusion of pulmonary function testing will be recorded on a specific source data worksheet and captured in the eCRF.

4.2.1.2 Emergency procedures

There are no special emergency procedures to be followed.

4.2.1.3 Additional treatment

Medications allowed to control acute exacerbations as medically necessary during the treatment period:

- PRN albuterol HFA inhalation aerosol (MDI) provided by BI.
- Temporary additions of oral steroids are allowed during the treatment portion of the study. Pulmonary function testing visits should not occur within seven days of the last administered dose of an addition of oral steroids. Pulmonary function testing visits may be postponed up to 14 days to meet this restriction. Subsequent visits will be scheduled according to the patient's regular schedule.
- Temporary additions of theophylline preparations are allowed during the treatment portion of the study. Pulmonary function testing visits should not occur within seven days of the last dose. Pulmonary function testing visits may be postponed up to 14 days to accommodate this restriction. Subsequent visits will be scheduled according to the patient's regular schedule.
- The use of antibiotics is not restricted and may be prescribed as medically necessary for exacerbations and / or infections. If antibiotics are prescribed for a respiratory infection prior to pulmonary function testing visits, the visit will be postponed for at least two days but not more than seven days after the last dose is given. Subsequent visits will be scheduled according to the patient's regular schedule.

Oral steroids, theophylline preparations and antibiotics will not be provided by BI.

4.2.2 Restrictions

4.2.2.1 Restrictions regarding concomitant treatment

The following table provides an overview of permitted and restricted medication over the different study periods.

Table 4.2.2.1: 1 Permitted medications and medications restrictions

| Drug Class | Sub-class | Prior to study | Study Period | | |
|------------------------|--|----------------|-------------------------|-------------------------|------------------|
| | | | Screening Period | Treatment Period | Follow up Period |
| Corticosteroids | Inhaled corticosteroids (not allowed for 2 weeks prior to V1) | Permitted | NOT permitted | NOT permitted | Permitted |
| | Oral corticosteroids (not allowed for at least 6 weeks prior to V1; permitted intermittently during the treatment phase in a case of COPD exacerbation) | Permitted | NOT permitted | NOT permitted | Permitted |
| | Injected Corticosteroids – local administration (for treatment of e.g. bursitis) | Permitted | Permitted | Permitted | Permitted |

Table 4.2.2.1: 1 Permitted medications and medications restrictions (cont.)

| Drug Class | Sub-class | Prior to study | Study Period | | |
|--------------------------|--|---|---|----------------------|----------------------|
| | | | Screening Period | Treatment Period | Follow up Period |
| β-adrenergics | Inhaled short-acting β-adrenergics | Permitted ¹ | Rescue ¹ | Rescue ¹ | Permitted |
| | Inhaled long-acting β-adrenergics (b.i.d.) (e.g. formoterol / salmeterol) | Permitted ¹ (w/o 48 hrs. prior to V1) | NOT permitted | NOT permitted | Permitted |
| | Inhaled long-acting β-adrenergics (q.d.) (i.e. indacaterol, olodaterol) | Permitted ¹ (w/o 1 wk prior to V1) | NOT permitted (w/o 3wks. prior to V2) | NOT permitted | Permitted |
| β-adrenergics | Oral and patch beta-adrenergics | Permitted ¹ (w/o 4 wks. prior to V1) | NOT permitted | NOT permitted | NOT permitted |
| | Beta blockers (If stabilized 6 wks. prior to V1) | Permitted | Permitted | Permitted | Permitted |
| Anti-cholinergics | Short-acting anticholinergics (inhalation aerosol, nasal spray) | Permitted ¹ | Permitted ¹ (w/o 8 hours prior to V2) | NOT permitted | Permitted |
| | Long-acting anticholinergics (b.i.d./q.d.) (i.e. tiotropium, aclidinium, glycopyrronium, umeclidinium, tio+olo) | Permitted (w/o 1 wk prior to V1) | NOT permitted (w/o 3 wks. prior to V2) | NOT permitted | Permitted |

Table 4.2.2.1: 1 Permitted medications and medications restrictions (cont.)

| Drug Class | Sub-class | Prior to study | Study Period | | |
|---------------------|--|---------------------------------------|--|------------------|------------------|
| | | | Screening Period | Treatment Period | Follow up Period |
| Combinations | ICS/LABA (b.i.d.) (*switch to LABA mono-product 2 weeks prior to V1, and then discontinue LABA at least 48 hrs prior to V1) (if switched to e.g. salmeterol, formoterol) | Permitted ¹ | NOT permitted* | Study medication | Permitted |
| | ICS/LABA (q.d.) (*switch to LABA mono-product 2 weeks prior to V1, and then discontinue at least 1 wk. prior to V1) (if switched to e.g. indacaterol, olodaterol) | Permitted | NOT permitted* | NOT permitted | Permitted |
| | ICS/SABA (*switch to SABA only 2 weeks prior to V1, and then discontinue SABA at least 8 hrs prior to V1) | Permitted ¹ | NOT permitted* | NOT permitted | Permitted |
| | short-acting anticholinergic/ SABA (*8 hrs. prior to V1) | Permitted ¹ | NOT permitted* | NOT permitted | Permitted |
| | Long-acting anticholinergics/long-acting β -adrenergics ² (e.g. glycopyrronium+indacaterol, umeclidinium+vilanterol) | Permitted (w/o 1 week prior to V1) | NOT permitted (w/o 3wks. prior to V2) | Study medication | Permitted |

Table 4.2.2.1: 1 Permitted medications and medications restrictions (cont.)

| Drug Class | Sub-class | Prior to study | Study Period | | |
|---------------|--|------------------------|------------------------|------------------------|------------------------|
| | | | Screening Period | Treatment Period | Follow up Period |
| Miscellaneous | Other investigational drugs (*1 month or 6 half-lives (whichever is greater) prior to V1) | NOT permitted* | NOT permitted | NOT permitted | NOT permitted |
| | Cromolyn sodium / nedocromil sodium (*if prescribed for non-asthma condition) | Permitted* | Permitted* | Permitted* | Permitted* |
| | Antihistamines, antileukotrienes (*if prescribed for non-asthma condition) | Permitted* | Permitted* | Permitted* | Permitted* |
| | Methylxanthines* (*if prescribed for non-asthma condition) | Permitted ³ | Permitted ³ | Permitted ³ | Permitted ³ |
| | Mucolytics (not containing bronchodilators; stabilized 6 wks. prior to V1) | Permitted | Permitted | Permitted | Permitted |
| | Phosphodiesterase type 4 (PDE-4) inhibitor ⁴ (e.g. roflumilast) | NOT permitted | NOT permitted | NOT permitted | NOT permitted |
| | Biologic or other immunomodulators | NOT permitted | NOT permitted | NOT permitted | NOT permitted |

Table 4.2.2.1: 1 Permitted medications and medications restrictions (cont.)

| | |
|----|--|
| 1. | Refer to Section 4.2.2.2 for washout period prior to PFTs. |
| 2. | Patients may be switched to q.d. LABA and short acting anticholinergic. Refer to Section 4.2.2.2 for washout period prior to PFTs. |
| 3. | For theophyllines: Refer to Section 4.2.2.2 for washout period prior to PFTs. |
| 4. | Patients currently using PDE-4-inhibitors (e.g. roflumilast) should not be enrolled and roflumilast should not be withdrawn for the purpose of enrolling in this study. Patients who were using roflumilast in the past may be included if their last use was a minimum of 3 months prior to Visit 1. In the event a patient with prior use of roflumilast is enrolled, past medical records are required to support and document why and when roflumilast was stopped. |

Medication restrictions for pulmonary function testing:

- Morning dose of trial medication should not be taken prior to test-day pre-dose PFT.
- At least a 2 week washout of inhaled steroids prior to PFTs at Visit 1. (Inhaled steroids are not allowed after Visit 1).
- At least an 8-hour washout of short-acting beta-adrenergic bronchodilators
- At least a 48-hour washout of long-acting beta-adrenergic bronchodilators (b.i.d.) prior to Visit 1 (not allowed between Visit 1 and 5).
- At least a 1-week washout of long-acting beta-adrenergic bronchodilators (q.d.) prior to Visit 1 and a 3-week washout prior to Visit 2.
- At least an 8-hour washout of short-acting anticholinergic bronchodilators prior to Visit 1 and 2 (not allowed during treatment periods)
- At least a 1-week washout of long-acting anticholinergic bronchodilators (b.i.d. or q.d.) prior to Visit 1 and a 3-week washout prior to Visit 2.
- At least a 4-week washout of oral and patch anticholinergics prior to Visit 1.
- At least a 24-hour washout of short-acting (b.i.d. or more frequent administration) theophylline preparations.
- At least a 48-hour washout of long-acting (q.d. administration) theophylline preparation.

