3. DESCRIPTION OF DESIGN AND TRIAL POPULATION

3.1 OVERALL TRIAL DESIGN AND PLAN

This is a randomized, double-blind, double-dummy, active-controlled, multi-center, parallel group, Phase IV study to show superiority in lung function of 12 weeks once daily treatment with orally inhaled tiotropium+olodaterol fixed dose combination (5µg/5µg) delivered by the Respimat[®] inhaler vs. 12 weeks twice daily orally inhaled treatment with fluticasone propionate+salmeterol fixed dose combination (250µg/50µg) delivered by the Diskus[®] inhaler in patients with Chronic Obstructive Pulmonary Disease (COPD).

The study will consist of a screening and run-in period of at least 4 four week duration, a 12-week randomised treatment period and a three week follow up period.

After signing Informed Consent (IC) at Visit 0 and completing an initial screening visit (Visit 1), patients enter a four-week screening (baseline) period to ensure clinical stability (i.e. no exacerbations). Patients who meet all inclusion criteria and do not present with any of the exclusion criteria will be randomised into the 12-week treatment period (at Visit 2) in which they will be assigned randomly to one of two treatments. An interactive response technology (IRT) system will be used for randomisation to treatment in this trial and for allocation of medication to patients throughout the treatment period. Additional clinic visits will be scheduled after 6 and 12 weeks of treatment (Visits 3 and 4). A follow-up visit (Visit 5) will be scheduled approximately three weeks after the last dose of study medication.

Individual patient participation is concluded when the patient has completed the last planned visit. The “last-patient-last-visit-primary-endpoint” is the last scheduled primary endpoint visit at Week 12 completed by the last patient. The end of the trial is defined as “last patient out”, i.e. last scheduled visit completed by the last patient.

All randomised patients who withdraw prematurely are encouraged to have an end of treatment (EOT) visit and a follow-up visit, three weeks after the EOT visit.

Site staff will contact the patients by telephone approximately one to two days prior to scheduled PFT visits (Visits 2, 3 and 4) to remind them of medication washout and any other requirements in preparation for the visit (see [Figure 3.1: 1](#)).

[figure not shown]

Figure 3.1: 1 Study design flow diagram

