- Approximately 1-2 days prior to visits 2, 3 and 4, a telephone contact will be made to each patient in order to remind him/ her of the medication restrictions and to adhere to the correct time of intake of the trial medication administration the day before the site visit. Please refer to [Section 4.1.4](#) (“trial medication administration at home”). It should be pointed out that trial medication administration on the site visit day will only be performed on site.
- Dosing of trial medication is to be performed on timing pre-determined at Visit 2 (i.e. day 1) (\pm 30 minutes).
- At Visit 4 only, site staff will make the “Trial Medication Termination” call to the IRT. At Visit 4, rescue medication must be returned and all patients can go back to normal medications after this visit.

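### The b.i.d. LABA bullet in protocol Section 4.2.2.1 extends the bar to Visit 5, but Table 4.2.2.1:1, Section 6.2.2 and Section 3.2 all end it with treatment

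*Protocol*

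**What the plan says.** Section 4.2.2.1 of the protocol gives the medication rules twice: as a table by study period, and then as a list of restrictions for pulmonary function testing (PFT).

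- **List, b.i.d. LABA bullet:** "At least a 48-hour washout of long-acting beta-adrenergic bronchodilators (b.i.d.) prior to Visit 1 (not allowed between Visit 1 and 5".
- **Table 4.2.2.1:1, inhaled b.i.d. LABA row.** The columns run prior to study, screening, treatment, follow-up. The row ends "w/o 48 hrs. prior to V1) | NOT permitted | NOT permitted | Permitted".
- **Table 4.2.2.1:1, b.i.d. ICS/LABA row.** The screening, treatment and follow-up cells read "NOT permitted* | Study medication | Permitted".
- **Section 6.2.2:** "At Visit 4, rescue medication must be returned and all patients can go back to normal medications after this visit".
- **Section 3.2** explains why LABAs, anticholinergics and inhaled steroids are restricted, and places that restriction in the treatment phase.

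The inhaled-steroid bullet in the same list adds that these drugs are barred after Visit 1 and gives no end point. The table permits them in follow-up.

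**The concern.** The bullet and the table give opposite answers for the same drug class over the same weeks, and neither text says which prevails. This is an instruction about patient care. The patients have moderate to severe COPD, their trial medication has stopped, and they have handed back the supplied rescue inhaler. A site that works from the bullet would keep a patient off a usual b.i.d. LABA until Visit 5. A site that works from the table could have a deviation recorded against the bullet for doing what the rest of the protocol allows.

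**Working it through.** The plan has no figure to reproduce. The check is a comparison of texts, followed by a day count.

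**1. Does the bullet's bar really cover follow-up?** Sections 6.1 and 6.2.3 define follow-up as the 21 days after treatment, ending with Visit 5. The table's follow-up column therefore cannot mean time after Visit 5. Even if the word between leaves out the two visits themselves, the interval from Visit 4 to Visit 5 lies inside the bar. The conflict is literal.

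**2. Which text is wrong?** Four things point to the bullet.

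- The table carries a bar into follow-up where one is meant. The row for oral and patch beta-adrenergics ends "w/o 4 wks. prior to V1) | NOT permitted | NOT permitted | NOT permitted". PDE-4 inhibitors and biologics are also barred in all periods. The b.i.d. LABA row is not.
- The list concerns spirometry. Section 3.1 names the "scheduled PFT visits (Visits 2, 3 and 4"), Visit 1 has the screening test, and the Flow Chart shows no PFT at Visit 5. A bar beyond Visit 4 protects no measurement.
- The neighbouring bullets for once-daily LABAs and long-acting anticholinergics carry no bar to Visit 5, and the bullet for short-acting anticholinergics confines its bar to treatment. Singling out b.i.d. LABAs for the longest bar has no stated reason.
- Sections 3.2 and 6.2.2 agree with the table.

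**3. How long is the interval?** Section 4.1.4.1 fixes its start: "The last administration of the study medication will be taken at the clinic at Visit 4 (EOT"). The Flow Chart puts Visit 4 at Day 84 (window ±3 days) and Visit 5 at Day 105 (window ±7 days).

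- Last trial dose to Visit 5: 105 − 84 = 21 days.
- End of the 24-hour spirometry (84 + 1 = Day 85) to Visit 5: 105 − 85 = 20 days.
- Range within the windows, if both visits are counted from Day 1 as Section 6.1 says: shortest (105 − 7) − (84 + 3) = 98 − 87 = 11 days; longest (105 + 7) − (84 − 3) = 112 − 81 = 31 days. This leaves out the postponement of a PFT visit by up to 14 days that Section 4.2.1.3 allows.

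**4. Does it reach the analysis?** SAP Table 6.2:1, rule D2, judges prohibited medication against Table 4.2.2.1:1, with a decision if use falls in the week before Visit 2 or Visit 4. Rule D1 looks at washout for Visits 2 and 4. All primary and secondary endpoint data are complete when the Visit 4 spirometry ends. A LABA taken in follow-up touches none of these.

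**The case against.** The best reply is that the protocol already answers the question. The bullet stands under a PFT heading, the table is the stated overview by study period, and Section 6.2.2 is an explicit instruction at Visit 4. Against these stands one parenthesis, quite possibly a 5 typed for a 4, and most sites would probably follow the table. This is fair and it sets the weight of the point. It does not remove the conflict: the parenthesis is an outright prohibition with visit numbers, not a washout time. The amendment log, as shown, records corrections to this table but none to this bullet.

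Three stronger readings are tempting, and the documents support none of them.

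- *A reader might infer that patients are left without a bronchodilator.* They are not. The table permits short-acting beta-agonists, once-daily LABAs and long-acting anticholinergics in follow-up.
- *A reader might infer that the bar is deliberate, to keep the 21-day residual effect period for adverse events clean.* The protocol does not say so, and the table permits olodaterol and tiotropium in that same period.
- *A reader might infer that early discontinuers need a rule of their own*, because Section 3.1 says only that "All randomised patients who withdraw prematurely are encouraged to have an end of treatment (EOT) visit". They do not. Section 6.2.2 already ends the treatment period at EOT, and Flow Chart note 3 places the EOT visit at the time of discontinuation. The Visit 4 PFT cell does not carry note 3, and SAP Section 6.6.1 discards data from visits more than one day after study medication stops. A clause holding such a patient off a LABA while waiting for an EOT visit would recreate the problem.

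**Conclusion.** The bullet is wrong as written: it extends the b.i.d. LABA bar over a follow-up period in which the table and Section 6.2.2 allow these drugs. The size is nominally 21 days per patient, for those whose usual maintenance is a b.i.d. LABA. The documents do not give the number of such patients, nor do they show that any site would apply the bullet over the table. The day count assumes the nominal schedule. Endpoints, analysis sets, alpha and power are unaffected. This is a minor correction, worth making because it concerns treatment and costs a few words.

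**What to change.** In the b.i.d. LABA bullet, replace the parenthesis with: *(not allowed from Visit 1 until the end of the treatment period, i.e. completion of Visit 4/EOT; see Table 4.2.2.1:1)*. Give the inhaled-steroid remark in the same list the same end point, so that the two agree with each other and with the table's b.i.d. ICS/LABA row.

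The cost is two wording edits in one list, made in the next amendment or in a clarification letter to sites. No procedure, data collection or analysis changes.
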